15.5.1.2 Option to Remove P30-pp65 from vaccine

If the 200 µg/peptide/dose is determined to not be safe, consideration will be given to the removal of the P30-pp65 component of the vaccine.

Sera collected post-vaccination will be analyzed for drug hypersensitivity (histamine) or CRS (Th1 cytokines). If CRS is demonstrated, P30-pp65 will be removed from the vaccine, the data will be evaluated and the protocol will be

amended in consultation with the FDA. This is based on our experience with the PERFORMANCE trial (NCT02864368) where we found that pp65-specific memory T cells in the CMV seropositive patient stratum were likely mediating pp65 long peptide vaccine-specific toxicity. Therefore, removal of pp65-P30 will likely prevent toxicity in this patient population.

15.5.1.3 Expansion at MTD

Once the MTD is determined for CMV seropositive and CMV seronegative patients, additional patients will be treated at that dose level..

15.5.2 Overall Toxicity Monitoring Guidelines

With vaccinations potentially being administered through day 140, we will be monitoring within each stratum for the occurrence of unacceptable toxicities throughout vaccine treatment.

Tabulated below ([Table 4](#)) are the conditions under which accrual to a stratum will be temporarily suspended and data carefully reviewed to determine if accrual should be continued or terminated, and whether elements of the treatment regimen should be modified. Accrual will also be suspended whenever a death occurs that is possibly, probably, or definitely related to vaccine treatment.

Table 4: Conditions for Temporary Accrual Suspension

Number of Patients Within CMV Stratum Treated at a Particular Dose Level	Number of patients with unacceptable toxicity
0-6	≥2
7-9	≥3
10-14	≥4
≥15	≥5

15.5.3 Other AE Summaries

Ultimately, AEs will be tabulated in different ways for the manuscript summarizing the results of this study, annual reports for the SOCOMM, and the final report included within ClinicalTrials.gov. All patients who receive an initial vaccination will be included in these summaries.

- For the summary of AEs and SAEs within the ClinicalTrials.gov report, the percentage of patients who experience each type of AE regardless of attribution will be summarized.
- For the manuscript, AEs that are possibly, probably, and definitely treatment-related will be summarized. For each type of toxicity, the maximum grade experienced by each patient will be summarized with frequency distributions. Toxicity experienced with vaccines 1-5 may also be summarized separately from those experienced with vaccines 6 and 7.
- Two tabulations will be generated for review by the SOCOMM including one that includes all toxicities regardless of attribution, and another that includes

only toxicities that are possibly, probably, and definitely related to study regimen. For each of these tabulations, the maximum grade of each type of toxicity experienced by each patient will be summarized with frequency distributions.

15.6 Secondary Objectives

Secondary objectives include an assessment to assess the immunogenicity of P30-tethered EphA2, CMV pp65, and survivin, and to describe the survival and PFS of patients treated. The analyses of immunogenicity described below will focus primarily on those patients treated at the MTD.

Analyses proposed for secondary analyses assume methods appropriate for normally distributed data are appropriate. If underlying assumptions for planned analyses are violated, plans will be modified. Alternative analytic methods may also be considered to assess the robustness of inferences.

15.6.1 Secondary Objective: Tumor Antigens (pp65) After Priming Vaccination

Objective: To assess whether pp65-specific polyfunctional T cells increase after priming vaccination with P30-linked pp65 peptide

Analysis Set: Analyses will be conducted in 2 different datasets:

- i. All CMV seropositive patients treated at the CMV seropositive MTD who have day 1 (pre-vaccine #1), day 22 (post-vaccine #5) and day 84 (post-vaccine #6) PBMCs collected, and
- ii. All CMV seronegative patients treated at the CMV seronegative MTD who have day 1, day 22 and day 84 (post-vaccine #6) PBMCs collected.

Outcome: For analyses associated with pp65 among CMV seropositive patients, the outcome is mean fold increase in pp65-specific T cells between day 1 and 22, and the mean fold increase in pp65-specific T cells between day 1 and 84.

For analyses associated with pp65 among CMV seronegative patients, the outcome is percentage of patients who develop pp65-specific polyfunctional T cells due to vaccination between day 1 and 22, and the percent of patients who develop pp65-specific polyfunctional T cells due to vaccination between day 1 and 84.

Hypothesis: Vaccination with pp65 tethered to P30 will increase the number of pp65-specific CD8⁺ polyfunctional T cells over baseline (pre-vaccine day 1).

Analysis Plan: Among CMV seropositive patients, a one-sample t-test will assess the mean fold increase in pp65-specific T cells between day 1 and day 22.

Among CMV seronegative patients, the proportion of patients with a pp65-specific response between day 1 and day 22 will be estimated.

Similar analyses will be conducted for the change between day 1 and day 84. Analyses for the change between day 1 and day 84 will be limited to those who receive all of the initial 5 vaccines. Additional analyses will focus on patients who receive vaccine #6 and #7 without completion of all of the 5 initial vaccines.

Power Analysis: Within the ERADICATE study (Pro00000580), the mean (SD) fold change in 3-function polyfunctionality among CMV seropositive patients is 1.93 (1.38). Assuming normality, there is 78% power to detect a similar increase in the fold change in CD8+ with at least 6 CMV seropositive patients ($\alpha=0.05$).

Prior studies of pp65 mRNA-loaded DC vaccine conducted at Duke in CMV seronegative patients using this technique showed a pp65-specific T cells response rate of 2.5%. If the true response rate among CMV seronegative patients treated with the P30-EPS vaccine is similar, the expected number of responders is 0. Tabulated below is the probability of observing 1 or more responders out of 12 CMV seronegative patients as a function of the true (and unknown) response rate. The probability of observing 1 or more responders will be greater if more than 12 CMV seronegative patients are evaluable for this endpoint.

True Response Rate	Probability of Observing 1 or more Responders
2.5%	0.26
5%	0.46
10%	0.72
15%	0.86
20%	0.93
25%	0.97
30%	0.99

15.6.2 Secondary Objective: Tumor Associated Antigens (EphA2 and survivin) After Priming Vaccination

Objective: To assess whether EphA2- and survivin specific polyfunctional T cells increase after priming vaccination with P30-linked EphA2 and survivin peptides

Analysis Set: All patients treated at the MTD who have day 1, day 22 and day 84 PBMCs collected

Outcome: For analyses associated with EphA2 and survivin, the mean fold increase in EphA2- and survivin-specific T cells between day 1 and day 22 and the mean fold increase between day 1 and day 84.

Hypothesis: Vaccination with EphA2 and survivin linked to P30 will increase the number of EphA2- and survivin-specific CD8⁺ polyfunctional T cells over baseline (pre-vaccine day 1).

Analysis Plan: A one-sample t-test will assess whether there is a significant mean fold increase in EphA2- and survivin-specific T cells between day 1 and day 22.

A similar analysis will explore the change between day 1 and day 84.

Power Analysis: Within the ERADICATE study (Pro00000580), the mean (SD) fold change in 3-function polyfunctionality among CMV seropositive patients is 1.93 (1.38). Assuming normality, there is >99% power to detect a similar increase in the fold change in EphA2-, and survivin specific T cells with 18 or more patients ($\alpha=0.05$).

If the MTD among CMV seropositive patients is different from the MTD for CMV seronegative patients, then these analyses may be conducted separately within the two strata.

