12.3 End of Treatment

If a patient progresses or once all vaccinations are completed, the treatment phase of the study will be over. Patients will then be followed for serious adverse events (SAEs) for 30-days after their final treatment intervention. Concomitant medication will not be tracked after the final treatment intervention. An attempt will be made to collect immune monitoring blood at the time of progression (for patients who completed all vaccines without prior progression). If a patient undergoes other clinically indicated resections or biopsy while still being followed, the study team may request a sample of leftover tissue for DNA and RNA analysis.

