15.6.3 Secondary Objective: Tumor Antigens (pp65) After Booster Vaccination

Objective: To assess whether pp65-specific polyfunctional T cells increase after booster vaccination with P30-linked pp65 peptide

Analysis Set: Analyses will be conducted in 2 different datasets:

- i. All CMV seropositive patients treated at the CMV seropositive MTD who have day 84 and day 140 PBMCs collected, and
- ii. All CMV seronegative patients treated at the CMV seronegative MTD who have day 84 and day 140 PBMCs collected.

Outcome: For analyses associated with pp65 among CMV seropositive patients treated at the CMV seropositive MTD, the outcome is mean fold increase in pp65-specific T cells between day 84 and 140.

For analyses associated with pp65 among CMV seronegative patients treated at the CMV seronegative MTD, the outcome is percent of patients who develop pp65-specific polyfunctional T cells due to vaccination between day 84 and day 140.

Hypothesis: Booster vaccination with pp65-linked P30 will increase the number of pp65-specific CD8⁺ polyfunctional T cells on day 140 over day 84.

Analysis Plan: Among CMV seropositive patients treated at the CMV seropositive MTD, a one-sample t-test will assess the mean fold increase in pp65-specific T cells between day 84 and day 140.

Among CMV seronegative patients treated at the CMV seronegative MTD, the proportion of patients with a pp65-specific response between day 84 and day 140 will be estimated.

Analyses described will be conducted among patients who complete all of the first 5 vaccines. Analyses will be conducted separately for patients who receive vaccine #6 and #7 without completion of the first 5 vaccines.

15.6.4 Secondary Objective: Tumor Associated Antigens (EphA2 and survivin) After Booster Vaccination

Objective: To assess whether EphA2- and survivin-specific polyfunctional T cells increase after booster vaccination with P30-linked EphA2 and survivin peptides

Analysis Set: All patients treated at the MTD who have day 84 and day 140 PBMCs collected

Outcome: For analyses associated with EphA2 and survivin, the outcome is mean fold increase in EphA2- and survivin-specific T cells between day 84 and day 140

Hypothesis: Booster vaccination with EphA2 and survivin linked to P30 will increase the number of EphA2- and survivin-specific CD8⁺ polyfunctional T cells on day 140 over day 84.

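### The Day 1 to Day 22 immunogenicity analyses exclude patients who have both samples but no Day 84 sample, so a later event decides who is counted

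*Combined protocol and SAP*

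**What the plan says.** Section 15.6.1 defines two pp65 priming datasets, one per CMV stratum. The seronegative one reads "All CMV seronegative patients treated at the CMV seronegative MTD who have day 1, day 22 and day 84", meaning PBMC samples at all three. The seropositive one sets the same condition: a Day 1 sample plus "day 22 (post-vaccine #5) and day 84 (post-vaccine #6) PBMCs collected, and". Section 15.6.2 does likewise for EphA2 and survivin: "All patients treated at the MTD who have day 1, day 22 and day 84 PBMCs collected".

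Each section then applies its set to two outcomes, the change from Day 1 to Day 22 and the change from Day 1 to Day 84. For seropositive patients the first is tested so: "a one-sample t-test will assess the mean fold increase in pp65-specific T cells between day 1 and day 22". No separate set is given for it. The one condition that 15.6.1 attaches to a single comparison concerns the later one: "Analyses for the change between day 1 and day 84 will be limited to those who receive all of the initial 5 vaccines".

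This wording controls. Section 15.2 says the objective-specific sections describe the patients analysed, and Section 9.4 refers evaluability for secondary endpoints to Section 15.6.

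Other sections ask only for the samples that bound their own interval. The seronegative booster set in 15.6.3 is "All CMV seronegative patients treated at the CMV seronegative MTD who have day 84 and day 140 PBMCs collected", and the TCR set in 15.7.1 needs only a baseline and a post-vaccine 5 sample.

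**The concern.** The Day 1 to 22 change is fully determined by two samples. Requiring a third, taken about two months later, makes inclusion depend on what happens after the endpoint has been measured.

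That later event is tied to the patient's course. Section 12.3 states: "If a patient progresses or once all vaccinations are completed, the treatment phase of the study will be over". Under Table 3 (footnote 5) and Section 12.3, immune blood at progression is attempted at a vaccine visit or after all vaccines are complete. A patient who progresses or withdraws between Day 22 and Day 84 would therefore normally have no Day 84 sample, and a completed Day 22 result goes unused.

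Two things are at stake. The Day 22 estimates would describe patients who stayed until Day 84 rather than patients who were primed and sampled. Precision is also given up in a small sample, most visibly among the roughly 8 seropositive patients expected at the MTD.

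**Working it through.** **Inputs.** From Section 15.9: 24 patients at the MTD, two-thirds seronegative, about 75% giving Day 140 data. From 15.6.1 and 15.6.2: fold change mean 1.93, SD 1.38, alpha 0.05; 78% power at n = 6; more than 99% at n = 18; a seronegative response table at n = 12. The documents give no Day 84 retention figure.

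**1. The plan's own figures.**
- Exact one-sample t-test, two-sided, noncentrality √n × 1.93/1.38 (null value 0): n = 6 gives 0.7805 and n = 18 gives 0.9998. Both match. A null value of 1 would give 0.27 at n = 6; which null is right is a separate question.
- 1 − (1 − p)^12 for p = 2.5%, 5%, 10%, 15%, 20%, 25%, 30% gives 0.262, 0.460, 0.718, 0.858, 0.931, 0.968, 0.986. All match the table.
- 18/0.75 = 24, as stated.

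**2. What the planning numbers represent.** 24 × 2/3 = 16 seronegative and 8 seropositive. 75% of 8, 16 and 24 is 6, 12 and 18. The power statements therefore already assume Day 140 availability, and a set restricted to Day 84 should not fall below them.

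**3. Patients lost, assuming a constant dropout rate.** Retention at day t is 0.75^(t/140): 0.956 at Day 22 and 0.841 at Day 84.

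| | Day 22 | Day 84 | Lost |
|---|---|---|---|
| All (24) | 22.9 | 20.2 | 2.7 |
| Seronegative (16) | 15.3 | 13.5 | 1.8 |
| Seropositive (8) | 7.65 | 6.73 | 0.9 |

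The loss is 2.7/22.9 = 12%.

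**4. Range without that assumption.** If Day 84 retention lies between 75% and 100%, the restricted set holds 18 to 24 patients. The loss is 0 at one end. At the other it is 24 − 18 = 6, if everyone gave a Day 22 sample.

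**5. What those patients are worth.**
- Seropositive, on the plan's power basis: n = 6, 7, 8 give 78%, 87%, 92%.
- Seronegative, chance of at least one responder at a true rate of 10%: n = 12, 13, 15, 16 give 0.72, 0.75, 0.79, 0.82. At 2.5%: 0.26, 0.28, 0.32, 0.33.

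**6. Selection, with assumed response rates.** Take 16 seronegative patients with Day 22 data, 12 of whom also have Day 84, and a 20% rate in those 12. The restricted set estimates 20%.
- If the other 4 respond at 10%, the rate among all 16 is (12 × 0.20 + 4 × 0.10)/16 = 17.5%.
- If none of the 4 respond, it is 2.4/16 = 15%.
- If the 4 respond at 30%, it is (2.4 + 1.2)/16 = 22.5%.

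The error can go either way.

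**The case against.** The strongest defence is that a common set is a recognised choice, because it lets the Day 22 and Day 84 changes be compared in the same patients. That has merit, but the plan does not give it as a reason, and a sensitivity analysis can serve the purpose. The five-vaccine condition on the Day 84 analysis does not prove that the Day 22 restriction was a slip. The contrast with the booster and TCR sets shows only that the sections are inconsistent.

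A reader might infer that the Day 22 result is inflated because those who stay are doing better. The documents do not settle this. Sections 9.1 and 9.1.5 say steroids may blunt the response, and 12.5.1 lists a steroid need that cannot be brought down as a ground for withdrawal; losing such patients could raise the estimate. But Sections 7.2.2 and 9.1.4 report that, in a related pp65 vaccine trial, patients with Grade 3 reactions had measurable cellular responses. Losing toxicity withdrawals could then lower it.

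A reader might also infer that everyone lost is an early failure. That is not so. Sections 9.1.6 and 12.5.1 allow removal for non-compliance, administrative issues, infection or the patient's own choice, and a draw can simply be missed. Progression found at the Day 84 visit need not lose the sample, since Table 3 (footnote 5) provides for an attempted draw.

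Some text leans toward inclusion. The Section 8 endpoint table and the synopsis put no Day 84 condition on the Day 22 outcome, Sections 12.5.3 and 15.5.1.1 keep replaced patients in other analyses, and Section 15.6 allows alternative methods. None of it overrides the defined sets.

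**Conclusion.** The point holds for all three priming sets: both pp65 strata and EphA2/survivin. Followed as written, the plan discards completed Day 1 to 22 data because of a later event. The expected loss is about 3 of 24 patients at the MTD (roughly 2 seronegative and 1 seropositive). This rests on the plan's rough 75% figure for Day 140 and an assumed constant dropout rate; the range is 0 to 6 if Day 84 retention lies between 75% and 100%. Bias is possible, with its direction unknown.

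It would go too far to call the analyses underpowered on the plan's terms. The planning numbers of 6, 12 and 18 already allow for loss to Day 140, so the cost is precision above that basis. The affected endpoints are secondary, Section 15.9 places the primary correlative analysis at Day 140, and the primary safety analysis and dose decisions are untouched. The change is worth making because it is nearly free, not because the trial's main conclusion depends on it.

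**What to change.** In Sections 15.6.1 and 15.6.2, define one set per comparison:
- **Day 1 to 22:** all patients treated at the MTD (by stratum for pp65) with evaluable Day 1 and Day 22 PBMCs.
- **Day 1 to 84:** all such patients with evaluable Day 1 and Day 84 PBMCs, plus, in 15.6.1, the five-vaccine condition already stated.
- **Sensitivity analysis:** the present three-sample set, for comparing time points in the same patients.

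Report how many patients have a Day 22 but no Day 84 sample, with reasons. Check that the wording agrees with Sections 9.4, 12.5.3 and 15.5.1.1.

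The cost is about two sentences of text, with no new samples, visits or patients. Section 10.1.4 shows that patients have already been treated, so the change should be made before the immune results are examined; otherwise the set could appear to have been chosen with the data in view.

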7.2.2 Clinical Experience

Due to routine childhood vaccination with tetanus toxoid, universal class II binding peptides from tetanus toxoid (P30 and P2 epitopes) have a well-established safety record and pre-existing immunity to the P2 and P30 epitopes is highly likely in all patients. The tetanus toxoid-derived P2 and P30 class II helper epitopes have long history of being used as CD4⁺ helper epitopes and have been combined with other antigens as separate peptides [51] and as a fusion peptides in clinical trials [26, 52].

pp65

Our group has 10 years of experience in vaccinating subjects with CMV pp65-LAMP loaded DCs. While the type of vaccination is different, our experience with CMV pp65-LAMP loaded DC vaccines is pertinent to this protocol. In the ATTAC trial (NCT00639639), patients were randomized to receive CMV pp65-LAMP DC vaccination following tetanus toxoid or unpulsed DC pre-conditioning at the vaccine site. In the ATTAC GM trial, patients were vaccinated with CMV pp65-LAMP DCs mixed with GM-CSF (Granulocyte macrophage colony-stimulating factor) [53]. In the ERADICATE study (NCT00693095), patients received CMV pp65-LAMP DCs and CMV-specific adoptive lymphocyte transfer [54]. In the REGULATE study (NCT00626483), patients received CMV pp65-LAMP DCs in combination with anti-CD25 monoclonal antibody (mAb) treatment (Basiliximab) to remove regulatory T cells (T_{Regs}). In the completed ELEVATE study under IND 16,301 (NCT02366728), subjects were treated with CMV pp65-LAMP DCs in combination with TMZ and either tetanus diptheria toxoid (Td) or unpulsed DC pre-conditioning. In the completed AVERT study under IND 16,301 (NCT02529072), patients received CMV pp65-LAMP DCs in combination with the anti-PD-1 mAb Nivolumab. The ongoing phase 2 “ATTAC II” trial (NCT02465268), a multi-site trial at the University of Florida and Duke, is investigating whether the addition of pp65-LAMP DC vaccines plus GM-CSF and Td to dose-intensified TMZ treatment is worthy of investigation in a larger phase 3 trial. In aggregate, we have given CMV pp65-LAMP DC vaccines to over 115 patients in combination with a number of agents. The CMV pp65-LAMP DCs have been well tolerated with no serious or off-target toxicities to date.

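### The stated 78% and >99% power for the fold-change t-tests hold only against a null of 0; if fold change is a post/pre ratio, power is about 27% (n=6) and 77% (n=18)

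*Combined protocol and SAP*

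**What the plan says.** For CMV seropositive patients, Section 15.6.1 specifies that "a one-sample t-test will assess the mean fold increase in pp65-specific T cells between day 1 and day 22", with a similar analysis for day 1 to day 84. The hypothesis is that cell numbers rise above the pre-vaccine day 1 level.

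The power paragraph takes its planning value from the ERADICATE study, where "the mean (SD) fold change in 3-function polyfunctionality among CMV seropositive patients is 1.93 (1.38"). Assuming normality and alpha 0.05, it concludes that "there is 78% power to detect a similar increase in the fold change" "with at least 6 CMV seropositive patients".

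Section 15.6.2 carries the same mean and SD over to EphA2 and survivin and says "there is >99% power to detect a similar increase in the fold change" with 18 or more patients. Sections 15.6.3 and 15.6.4 apply the same t-test to the change from day 84 to day 140, without a power statement.

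None of these sections gives a formula for fold change, a null value, or the sidedness of the test. Section 15.9 plans about 18 patients with Day 140 immune data out of 24 treated at the MTD, expects two-thirds of those treated to be seronegative, and refers the reader to Sections 15.6.1 and 15.6.2 for power.

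**The concern.** A one-sample t-test needs a reference value. If fold change is the later count divided by the earlier one, no change is 1, and 0 would mean that every antigen-specific cell had disappeared. Power computed as though 0 were no change credits the trial with detecting the whole of 1.93, not the 0.93 that lies above baseline.

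Two things are at stake. First, a non-significant pp65 result in about six seropositive patients would be judged against a stated power near 80%, and could be taken as evidence that the vaccine is not immunogenic. Second, because the analysis sections name no null, the reference value behind the power statement could pass into the test. A test of a ratio against 0 can be significant when the vaccine does nothing.

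**Working it through.** **Inputs.** Mean 1.93, SD 1.38, alpha 0.05, n = 6 (Section 15.6.1) and n = 18 (Section 15.6.2). The sidedness is not stated; two-sided is used below because it reproduces the plan's figure.

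**Formula.** Effect d = (1.93 − null)/1.38. Noncentrality = d × √n, with n − 1 degrees of freedom. Power is the probability that a noncentral t variable falls beyond the critical value, which is 2.571 for n = 6 and 2.110 for n = 18.

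**Step 1: reproduce the plan (null 0).** d = 1.93/1.38 = 1.399.
- n = 6: noncentrality 1.399 × 2.449 = 3.43; power 78.05%.
- n = 18: noncentrality 1.399 × 4.243 = 5.93; power 99.98%.

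Both match the stated 78% and >99%.

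**Step 2: null of 1 (ratio reading).** d = (1.93 − 1)/1.38 = 0.93/1.38 = 0.674.

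| n | Noncentrality | Two-sided power | One-sided power |
|---|---|---|---|
| 6 | 1.65 | 27.0% | 41.4% |
| 8 | 1.91 | 37.7% | 52.9% |
| 18 | 2.86 | 76.9% | 86.4% |

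The row for n = 8 is the seropositive third of the 24 patients in Section 15.9, if all are evaluable. Against a null of 1, two-sided, it takes 19 patients to reach 78% and 43 to reach 99%.

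**Step 3: could another calculation with no change at 1 give the stated figures?** None of those tried does.
- One-sided normal approximation on the raw scale, the most favourable raw-scale variant: 50.2% at n = 6 and 88.8% at n = 18.
- Log-normal with mean 1.93 and SD 1.38, tested on the log scale, two-sided: 28.8% and 80.1%.
- 1.93 taken as a geometric mean with the same coefficient of variation: 52.5% and 98.3% two-sided, 69.4% and 99.4% one-sided. The one-sided version passes 99% at n = 18 but does not give 78% at n = 6.

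**Step 4: precision at n = 6.** The half-width of the 95% CI is 2.571 × 1.38/√6 = 1.45. A trial that repeated the planning values exactly would report 1.93 ± 1.45, or 0.48 to 3.38, which includes 1.

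**Step 5: false positives if the ratio is tested against 0 and the vaccine has no effect.** The rate depends on the assumed distribution.
- Normal, true mean 1, SD 1.38 (d = 1/1.38 = 0.725): about 30% at n = 6 and 83% at n = 18.
- Log-normal with the planning coefficient of variation, 1.38/1.93 = 0.715: about 94% at n = 6 and >99.9% at n = 18.

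Every one of these is far above the nominal 5%.

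**The case against.** The strongest reply is that fold change is never defined. The outcome is usually called a fold increase, and only the power paragraphs and the synopsis speak of fold change. If 1.93 is a relative increase, (post − pre)/pre, or a mean change on a log scale, then 0 is the right null and 78% and >99% are correct. The exact match at null 0 fits that explanation as well as it fits a mistaken null, and the source data are not available to settle it. This stands, and it makes the error conditional. It does not make the plan complete, because the test cannot be run as specified without a null. The wording of a fold change that is 1.93, with a hypothesis of increase over baseline, reads more naturally as a ratio.

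A reader might infer that the analyst will test against 0 and almost always declare an increase. The documents do not support that. The analysis sections state no null, the hypotheses on a ratio scale imply 1, and at n = 6 the false-positive rate runs from about 30% to 94% depending on the model.

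A reader might also infer that the planning effect is optimistic, because in the source study "patients received CMV pp65-LAMP DCs and CMV-specific adoptive lymphocyte transfer" (Section 7.2.2). No document gives comparative fold changes that show the direction of any bias. It is a caveat about transportability and no more.

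Section 15.6 allows methods to change if assumptions are violated. That concerns distributional assumptions and does not supply a null. Finally, the plan says at least 6 patients, so 27% is the value at the minimum; 8 evaluable patients would give about 38%.

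**Conclusion.** The concern holds conditionally. The two stated power figures correspond to a null of 0. If fold change is the post/pre ratio, they should be about 27% (n=6) and 77% (n=18) two-sided, or 41% and 86% one-sided. This rests on the plan's own mean, SD, normality and alpha, and on the ratio reading. If the endpoint is a relative increase or a log-scale change, the stated figures stand and the defect is only that the endpoint and null are undefined. On either reading Sections 15.6.1 to 15.6.4 need correction before analysis.

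The consequence is limited to secondary immunogenicity endpoints. The primary safety objective, the 3+3 dose decisions and the cap of 36 patients do not depend on these power figures.

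**What to change.** 1. Define fold change by formula in Sections 15.6.1 to 15.6.4, and use one term throughout.
2. State the null (ratio 1, or mean log fold change 0) and the sidedness for each t-test.
3. If the endpoint is a ratio, restate the power as about 27% for 6 seropositive patients and about 77% for 18 patients (two-sided, alpha 0.05).
4. Present the seropositive pp65 result as an estimate with a 95% CI, noting a half-width of about 1.45 at n = 6 if the SD is 1.38.
5. If 1.93 is a relative increase or a log-scale change with null 0, say so and define the endpoint that way throughout. The power statements can then stay.
6. Note that the planning value comes from a study that also gave adoptive lymphocyte transfer, as a caveat without a stated direction.

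The cost is SAP wording and, on the ratio reading, a less favourable power statement. No patients, visits or samples are added.

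### The fold-increase t-tests leave the fold formula, null value, scale and zero-baseline rule undefined; on a raw post/pre ratio the EphA2 and survivin tests would over-declare increases, and the stated power would not hold

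*Combined protocol and SAP*

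**What the plan says.** Section 15.6.2 states for EphA2 and survivin: "A one-sample t-test will assess whether there is a significant mean fold increase in EphA2- and survivin-specific T cells", here from day 1 to day 22. The same approach is planned for day 1 to day 84, and Section 15.6.4 repeats the test for day 84 to day 140. For pp65, Section 15.6.1 says "Among CMV seropositive patients, a one-sample t-test will assess the mean fold increase in pp65-specific T cells between day 1 and day 22", and Section 15.6.3 says "a one-sample t-test will assess the mean fold increase in pp65-specific T cells between day 84 and day 140". Seronegative pp65 is treated differently: "Among CMV seronegative patients, the proportion of patients with a pp65-specific response between day 1 and day 22 will be estimated".

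The power statements in 15.6.1 and 15.6.2 rest on an earlier study in which the mean (SD) "fold change in 3-function polyfunctionality among CMV seropositive patients is 1.93 (1.38"). Assuming normality and alpha 0.05, they give 78% power with at least 6 seropositive patients and >99% with 18 or more patients. Section 15.9 expects 24 patients treated at the MTD, about 75% with Day 140 data (about 18), and two-thirds seronegative.

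The fallback in Section 15.6 is: "If underlying assumptions for planned analyses are violated, plans will be modified". It adds that other methods may be used to check robustness. Section 5.5 makes a similar allowance. Neither names a method or a trigger.

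**The concern.** A post/pre ratio cannot fall below zero and is usually right-skewed. Doubling (2.0) and halving (0.5) are equal and opposite changes, yet they average 1.25. Variation with no net direction therefore pushes the arithmetic mean above 1, and a t-test against 1 can read it as an immune response. If the baseline is zero the ratio does not exist, and a baseline near zero can dominate the mean. The plan avoids this for pp65 in seronegative patients by using a proportion, but it has no equivalent for EphA2 or survivin, which are tested in all patients at the MTD.

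At stake is whether a reported increase in antigen-specific T cells can be trusted, and whether the stated power belongs to the test that will be run.

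**Working it through.** **Inputs.** Mean 1.93, SD 1.38, n=6 and n=18, alpha 0.05 (15.6.1, 15.6.2). Sidedness is not stated; two-sided reproduces the plan's figure. Expected seropositive numbers from 15.9: 24 × 1/3 = 8 treated at the MTD, and 8 × 0.75 = 6 with Day 140 data.

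**1. The plan's own power.** Exact noncentral-t power for a one-sample test, with d = (mean − null)/SD:

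| Null | d | n=6 | n=18 |
|---|---|---|---|
| 0 | 1.93/1.38 = 1.399 | 78.05% | 99.98% |
| 1 | 0.93/1.38 = 0.674 | 27.0% | 76.9% |

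Both stated figures reproduce with a null of 0. With a null of 1, one-sided testing gives 41.4% and 86.4%, so no null-1 variant reaches either figure. For a post/pre ratio, no change is 1, not 0.

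**2. Fit of the normal model.** P(N(1.93, 1.38) < 0) = Φ(−1.399) = 8.1%, which is impossible for a post/pre ratio.

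**3. Bias with no change.** Assume a lognormal ratio with median 1 and the CV of the planning values: CV = 1.38/1.93 = 0.715, and log-SD = √ln(1 + 0.715²) = 0.643. The expected ratio is exp(0.643²/2) = 1.23. At log-SD 0.3 it is 1.05, and at 1.0 it is 1.65.

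**4. False-increase rate.** Simulated rate at which the two-sided 5% t-test of the raw ratio against 1 rejects upward when nothing changes (nominal 2.5%; 200,000 trials per case):

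| n | log-SD 0.3 | 0.448 | 0.643 | 1.0 |
|---|---|---|---|---|
| 6 | 2.3% | 2.1% | 2.0% | 1.7% |
| 8 | 2.7% | 2.8% | 2.8% | 2.7% |
| 12 | 3.7% | 4.3% | 5.1% | 6.5% |
| 18 | 5.2% | 7.0% | 9.9% | 14.7% |

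The t-test on the log ratio stays at about 2.5% in every cell. At n=6 to 8 the skewness offsets the bias in the mean.

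**5. Zero baselines.** The documents give no baseline frequencies. As an illustration only, assume Poisson counts with equal means before and after. The chance that at least one of 18 patients has a zero baseline is 93% at a mean count of 2, 60% at 3, 11.5% at 5 and 0.1% at 10.

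**6. Power on the log scale.** A lognormal model matched to 1.93 (1.38) has log mean ln(1.93) − 0.643²/2 = 0.451, geometric mean exp(0.451) = 1.57, and d = 0.451/0.643 = 0.70. Two-sided power is 28.8% at n=6 and 80.1% at n=18. Under this same model the raw test against 1 rejects upward in 21% at n=6 and 92% at n=18. The higher figure at n=18 comes with the inflated error rate of step 4.

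**The case against.** The strongest reply is that the plan never says raw scale or null of 1, and that its power figures fit a null of 0. That null is correct in two cases.

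- **Values are log fold changes.** The plan would then already be on the recommended scale. Nothing in the documents says so; the inputs are called fold changes.
- **Fold increase means (post − pre)/pre.** The stated power is then right, and negative values are legitimate down to −1 (the normal model puts Φ(−2.93/1.38) = 1.7% below that). But testing this quantity against 0 is the same test as post/pre against 1, so the inflation remains. The implied log-SD is √ln(1 + (1.38/2.93)²) = 0.448, and the false-increase rate at n=18 is about 7%.

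Three further points stand. The 0.643 comes from the spread between treated seropositive patients for pp65, so it mixes true response differences with assay noise and is borrowed for other antigens; hence the range. If the two MTDs differ, the EphA2 and survivin analyses may be split by stratum, and at n=12 the rate is 5.1%. The fallback clauses would permit a log or rank analysis, but leave the choice until the data are seen.

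A reader might infer that every fold-change test in the plan is inflated, or that zero baselines are known to be common. The documents support neither: seropositive pp65 has too few patients for material inflation, seronegative pp65 is analysed as a proportion, and no baseline frequencies or detection limit are given.

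**Conclusion.** The point holds as an under-specification with measurable consequences. The untransformed scale is inferred from the planning inputs, not stated.

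- **EphA2 and survivin, n about 18:** if fold change is a raw post/pre ratio tested against 1, false increases occur in about 10% of trials, or about 5% to 15% over assumed log-SDs of 0.3 to 1.0, against 2.5% nominal. This assumes symmetric variation on the log scale.
- **Seropositive pp65, n about 6 to 8:** no material inflation. The estimate is biased upward and the ratio is undefined at a zero baseline; how often that happens is an assumption.
- **Power:** 78% and >99% require a null of 0. For a post/pre ratio with a null of 1, two-sided power is 27% and 77%.

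It would go too far to say that the planned test is shown to be invalid, because the formula and null that would settle it are absent. These are secondary endpoints, and the primary safety objective is unaffected.

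**What to change.** In Sections 15.6.1 to 15.6.4, for seropositive pp65, EphA2 and survivin at all three intervals:

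1. Define fold change as post/pre.
2. Analyse log(post/pre), with values below detection set to a pre-specified floor.
3. Test mean log ratio = 0, and state the sidedness.
4. Report the geometric mean ratio with its 95% CI.
5. Name the Wilcoxon signed-rank test on the log ratios as the sensitivity analysis. Section 15.7.1 already uses that test for entropy.
6. Restate the power: about 29% at n=6 and 80% at n=18, two-sided, under a lognormal model matched to 1.93 (1.38).

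Other routes, such as a signed-rank primary analysis or a paired analysis of differences, would also avoid the problem; what matters is choosing one in advance. The cost is SAP wording and minor programming. The reported fold change will be smaller (geometric mean about 1.57 for the planning values, against 1.93), and the stated power will be less favourable, most visibly for seropositive pp65.
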